All consenting participants will have basic demographic and socioeconomic data collected by self-report via a survey administered by the study data collector at time of discharge. The study data collector will extract additional clinical data from the patient file. At time of discharge, participants will receive surgery follow-up instructions (Appendix A), including a set of warning signs for SSI and when to return to a health center, per standard of care. Additional human subjects contact will depend on study arm assignment. Individuals in Arm 1 will be visited at home by the sCHW who will administer the optimized SSI protocol via the mHealth device. Following the screening, the sCHWs will use the cell phone to photograph the surgical wound and record the GPS location of the visit. Individuals in Arm 2 will be phoned by the sCHW who will administer the SSI protocol over the phone. Individuals in Arm 3 will not have any additional contact beyond standard of care (Figure 1).

Figure 1:

BIOSTATISTICAL AND QUALITATIVE ANALYSIS:

Phase 1:

At the time of enrollment, study staff will administer a basic survey to record self-reported data on patient demographics (gender, age, weight, height, education level, location of residence, distance to hospital) and socioeconomic status (monthly household income, land ownership, cost of transport as a barrier to receiving health care). Study staff will also extract data from clinical charts on past medical history, type of surgery, time from surgery recommendation to operation, pre-operative antibiotic use/time, wound class, and any documented surgical complications. Clinical information will continue to be collected up to 90 days for any patients who are never discharged or for any patient who is readmitted for a surgical complication. For patients that are transferred to Kigali for tertiary care, we will use data collected routinely collected by the Right to Health Care program to complete their follow up information.

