Basic demographic and clinical data will be recorded at baseline by study staff, as described in phase 1. For Arms 1 and 2, addresses/phone numbers and availability will be documented for patient follow-up. At ten post-operative days (± 3 days), sCHWs will visit patients in Arm 1 at the address provided. The sCHW will be assisted by a local village CHW to identify the patients' homes. Once there, the sCHW will administer the SSI screening protocol with prompting from the phone, record responses into the phone, take a photo of the wound, and take GPS coordinates. Patients in Arm 2 will be phoned by the sCHW on the tenth post-operative day (± 3 days). The sCHW will administer the SSI screening protocol over the phone, prompted by the smartphone application to ask the appropriate questions. For both arms, patients identified as having an SSI will be referred back to KDH for care. These patients will also be asked a set of questions to assess for possible barriers to return of follow up. In this phase, patients will not receive financial support to return to the clinic. Patients not identified with SSI will be reminded of the warning signs and follow-up instructions. Patients still hospitalized at the hospitalized on their assigned screening day will be excluded from the study as they will not be eligible for the expected study follow up.

A patient tracker log at the hospital will be used to document patient return for follow-up care. The log will also document patients that self-present with potential SSI. Study staff will extract from the clinical chart the presence of an SSI, severity, treatment obtained, need for operative intervention, hospitalization, and/ or complications as recorded by a KDH GP. During the study period, clinical charts will be audited for completeness and GPs will be trained in data quality to ensure the accuracy of this clinical data. In addition, study staff will track process measures related to Arms 1 and 2.

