For Aim 5, we will report percent for each of the process measures with 95% confidence intervals. Process measures include: ability to find the patient's home (Arm 1), willingness to allow sCHW into home (Arm 1), percent of home visits completed (Arm 1), successful use of GPS (Arm 1), availability of phone (Arm 2), availability of patient when called (Arm 2), visits or calls completed on-time (Arms 1 and 2), percent of reports successfully transmitted via the application (Arms 1 and 2) and presentation to care upon referral (Arms 1 and 2).

Aim 6:

For Aim 6, we will identify potential predictors for failure to return, comparing those who were recommended in Arms 1 and 2 to return and did return to those who failed to return using logistic regression. Demographic and clinical predictors collected at enrollment will be used as potential predictors. All factors significant at the $\alpha=0.2$ significance level in the bivariate analysis will be considered for the multivariate analysis. We will build the final predictive model using backward stepwise regression, stopping when all factors remain significant at the $\alpha=0.05$. For those that fail to return to care, we will report their barriers to care using proportions and 95% confidence intervals. Responses to open ended questions will be transcribed and translated, and we will identify any unaddressed themes using a general inductive approach.

Aim 7:

For Aim 7, we will evaluate patient post-operative care behaviors using proportions and 95% confidence intervals. Responses to open ended questions will be transcribed and translated, and we will identify any unaddressed themes using a general inductive approach.

Aim 8:

For Aim 8, we will describe the median and ranges of expenses incurred by patients, stratified by whether or not the patient had a surgical site infection. We will also describe the median and range for the normal household expenditures and compare the care expenses relative to normal household expenditures.

Power Analysis:

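### Aim 6 picks predictors of non-return by stepwise selection from 11 to 14 candidates with about 22 to 45 expected non-returners, so noise variables can enter and real odds ratios will be overstated

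*Combined protocol and SAP*

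**What the plan says.** Under Analysis and Outcomes for Phase 2, Aim 6 models failure to return among referred patients, "comparing those who were recommended in Arms 1 and 2 to return and did return to those who failed to return using logistic regression". On the candidates it says: "Demographic and clinical predictors collected at enrollment will be used as potential predictors". Those with p below 0.2, in its words the "significance level in the bivariate analysis will be considered for the multivariate analysis". Then: "We will build the final predictive model using backward stepwise regression, stopping when all factors remain significant at the" 0.05 level.

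The plan gives no list or number of candidates for this model. The Phase 2 section refers back: "Basic demographic and clinical data will be recorded at baseline by study staff, as described in phase 1". The Phase 1 text under Biostatistical and Qualitative Analysis lists three groups:

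- demographics: "gender, age, weight, height, education level, location of residence, distance to hospital"
- socioeconomic status: "monthly household income, land ownership, cost of transport as a barrier to receiving health care"
- chart data: "past medical history, type of surgery, time from surgery recommendation to operation, pre-operative antibiotic use/time, wound class, and any documented surgical complications"

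The plan states no expected number of non-returners, cap on model size, shrinkage or internal validation. The Power Analysis section says that Aim 4 drove the Phase 2 sample size, so Aim 6 was not sized.

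**The concern.** After a selection of this kind, the p-values, confidence intervals and odds ratios of the surviving variables are read as if the model had been fixed in advance. They are not valid on that reading, because the same data chose the variables and estimated their effects. Variables that survive by chance look like findings. True predictors survive mainly when their estimates happen to be large, and others, possibly including distance to hospital, drop out by chance.

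The protocol counts the identification of barriers to follow-up among its benefits and has scale-up as its long-term goal. A misleading predictor model could therefore influence which women are targeted for extra support.

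**Working it through.** **The plan's own figure.** No power is stated for Aim 6. The only power figure is for Aim 4: 81% for 12% against 6%, 364 per arm, two-sided 0.05. A two-sample test of proportions with pooled variance gives 80.9%, so it reproduces for one intervention arm against Arm 3. It has no bearing on Aim 6.

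**Candidates.**
- Demographic: 7 listed. Gender is constant in caesarean patients, leaving 6.
- Clinical: 6 listed. Type of surgery is essentially constant, leaving 5.
- Demographic plus clinical: 6 + 5 = 11.
- Adding the 3 socioeconomic items: 14. The Aim 6 text names only demographic and clinical predictors, so whether these count is open.

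**Expected non-returners** (derived; the documents do not state them). Assume every patient in Arms 1 and 2 is contacted.
- Lower case, only true SSI cases referred: 2 × 55 = 110 cases. At the 80% return in the Power Analysis, 110 × 0.20 = 22.
- Upper case, taking the Aim 1 thresholds of 90% sensitivity and 80% specificity as achieved: true positives 110 × 0.90 = 99; false positives (728 − 110) × 0.20 = 124; referred 223. If 20% of all those referred fail to return, 223 × 0.20 = 45.

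Non-returners per candidate therefore run from 22/14 = 1.6 to 45/11 = 4.1. Multi-category variables such as education, residence and wound class would lower this.

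**Fault 1: noise variables.** If all k candidates are unrelated to return and independent, the chance that at least one reaches 0.05 is about 1 − 0.95^k: 43% for k = 11, 49% for k = 13 and 51% for k = 14. The stated procedure was also simulated (screen at 0.2, backward deletion to 0.05, half the covariates binary, correlation 0 or 0.3):

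| Null candidates | At least one kept |
|---|---|
| 8 | 28-30% |
| 12 | 42-44% |
| 13 | 45-49% |
| 14 | 45-48% |

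With one true predictor and 13 nulls, a noise variable was still kept in 46-49% of runs.

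The event count hardly matters here. With 13 independent null candidates the rate was 44.5% at 1.7 events per candidate, 46.9% at 3.5 and 47.7% at 16.9.

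**Fault 2: real effects.** One true predictor was simulated with an odds ratio of 1.5 per SD (an illustrative value, not from the documents) plus 13 nulls:

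| Non-returners | True predictor kept | Mean reported OR when kept |
|---|---|---|
| 22 | 38-39% | about 2.0 |
| 30 | 55% | 1.78 |
| 45 | 66% | 1.68 |

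Here the event count does matter.

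**The case against.** A reader might infer that the scarcity of non-returners is what produces the noise predictors. It is not: the rate is about the same at 17 events per candidate as at 2. It comes from the number of candidates tested at 0.05.

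A reader might also infer that about half of such analyses would report a noise predictor, without condition. That needs all or nearly all of 11 to 14 candidates to be unrelated to return. The protocol itself calls transport cost a known barrier, and with 8 null candidates the rate is 28-30%.

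Nor do the documents support saying that Aim 6's account of barriers rests on this model. Barriers are asked about at referral and in home interviews with non-returners, and are reported as proportions with confidence intervals and as themes. The regression concerns predictors only, which the plan calls potential.

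The event counts also depend on assumptions. Missed contacts would lower them, and a higher failure rate among false-positive referrals would raise them. The accuracy figures are thresholds that trigger revision of the screening protocol, not forecasts.

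Finally, much of the failure to keep a true predictor reflects a small sample, which no method cures. Five pre-specified null predictors still carry a 1 − 0.95^5 = 23% chance of at least one false positive.

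All of this stands, and it limits the point. It does not answer the absence of any allowance for selection, nor the exaggeration of the odds ratios that survive.

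**Conclusion.** The concern holds as two separate faults in a secondary aim. Uncontrolled testing of 11 to 14 candidates keeps at least one noise variable in about 40-50% of trials when all or nearly all are null, whatever the event count. With about 22 to 45 non-returners, a true odds ratio of 1.5 per SD is kept in about 38-66% of trials and, when kept, is reported at about 1.7-2.0.

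These sizes rest on full contact in Arms 1 and 2, 80% return among those referred, the two accuracy thresholds being met, and the illustrative effect. The method should be changed, but nothing in the Aim 4 comparison depends on it.

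**What to change.** - Replace the screen and backward deletion with one model of about four or five predictors, named by the investigators before return outcomes are examined by arm. It should include study arm (not among the candidates now described), distance or transport cost, and at least one clinical variable.
- Fit it by Firth or similarly penalised logistic regression, and report every coefficient with its confidence interval whatever the p-value.
- Report the remaining variables as unadjusted associations, labelled exploratory.
- If a predictive model is wanted, use a penalised fit and give bootstrap optimism-corrected performance.

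The cost is analysis wording only; data collection does not change. Variables off the short list get unadjusted results only. The change lowers the chance of a noise predictor (to about 23% if all five were null) and removes the exaggeration caused by selection. It does not add power: 22 non-returners over five predictors is still only 22/5 = 4.4 each, so the intervals will be wide and the report should say so.

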Specific Aim 8: We will assess the direct and indirect costs incurred by the mother and her family, stratified by whether or not she has a surgical site infection, and describe the burden of these costs relative to the overall financial expenditures of the household.

SUBJECT SELECTION AND ENROLLMENT:

This study will follow patients who received cesarean-section surgery at KDH and reside in Kirehe District. KDH is a 145-bed facility operated by the Rwanda Ministry of Health (RMOH) and supported since 2005 by the medical non-profit organization Partners In Health (PIH). The hospital serves a catchment area of 364,000 people, primarily residing in rural, outlying villages. In preliminary work, we conducted a chart review that showed that 7.3% of obstetric surgical patients and 3.1% of non-obstetric surgical patients returned to the hospital with an SSI. Based on regional literature, we expect the true rate of SSI in patients receiving surgery KDH to be 10-20%.²²

Phase 1

Participants will be adult (≥ 18 years) patients receiving cesarean-section surgery at KDH over a seven-month enrollment window. All patients receiving a cesarean section (c-section) surgery at KDH who reside in Kirehe district will be eligible and will be invited to participate on post-operative day 2. We anticipate enrolling 525 post-operative c-section patients who received surgery at KDH during the seven-month period. Patients will be enrolled consecutively. We will include patients from Mahama Refugee Camp when collecting information about the hospitalization and outcomes. However, these patients will not be asked to return for follow-up.

Phase 2

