We will continue to consecutively enroll participants on post-operative day 2 from the adult female patient population receiving c-section surgery at KDH during a 14-month period. Randomization into the three study arms will take place at time of discharge. We will enroll 1092 participants in this phase of the study, 364 per study arm. Once enrolled, there will be no special retention strategies so as not to interfere with the outcomes under investigation in Aim 4 (return to care) or Aim 5 (process measures describing the CHW-mHealth intervention implementation). If the patient is still in the hospital 10 days following surgery, they will be excluded from the study given the inability to be randomized properly to the three arms of this phase. We will include patients from Mahama Refugee Camp when collecting information about the hospitalization and outcomes. However, these patients will not be asked to return for follow-up.

Sealed study packets, prepared in advance, will be available at KDH. Each study packet will have the arm assignment for the patient, which will be randomly assigned during the preparation of the materials using a random number generator. Both the research staff and the patient will be unaware of the arm assignment during the consent process and the assignment will be revealed only after the patient has agreed to participate. In this phase, no participants will receive travel vouchers, to ensure appropriate comparison between the intervention and standard of care groups. Per standard of care, all patients will receive information on the signs of SSI and will be instructed to return as soon as any of these present. (Appendix A).

STUDY PROCEDURES:

This research includes two distinct phases. During the first phase, we will optimize the SSI screening protocol by piloting it among a cross-section of patients receiving surgery at KDH, Rwanda. In the second phase, we will randomize patients receiving surgery at KDH to one of three arms – standard of care and the two intervention arms. At the conclusion of the study, we will compare rates of return and severity of SSI at return among the three arms and report process indicators describing the implementation of the CHW-mHealth interventions in the two intervention arms. In this study, patients will be assessed at 10 days after their operation, as symptoms for SSI usually develop during the first 6-9 post-operative days.²³

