Patients in Arms 1 and 2, who are determined by the sCHW to have a suspected SSI and referred back to care, but fail to return back to care within one week will be identified. Data collectors will return to these patients' homes at 22-30 days post-operation to interview them on why they failed to return to care. The interviews will be semi-structured, including questions on established barriers to care and allowing for open-ended response. A random sample of patients in Arm 3 will be visited at home at 22-30 days post-operation by data collectors who will

interview them on their follow-up care procedures. The interviews will be semi-structured, including questions on standard care paths and allowing for open-ended response.

For a subset of 50 patients, we will administer at discharge a Financial Risk Protection Survey (Appendix D), an existing validated tool, to understand the total costs of care and the costs relative to normal household expenditures.

Analysis and Outcomes:

Aim 4:

For Aim 4, we will compare the proportion of patients who return for follow-up with an SSI in Arms 1 and 2 to Arm 3 (standard of care) using a two-sided, two-sample test of proportions at the $\alpha=0.05$ significance level. We will use a logistic regression model to assess the impact of study arm on measures of severity at presentation (for example, readmission to hospital), controlling for potential confounders collected at enrollment. All analyses will be completed as intention to treat, regardless of whether the patient had contact with the sCHW or was screened by the mHealth tool in Arms 1 and 2. For Aim 4, for Arms 1 and 2, we will report percent for each of the process measures (for example, percent of home visits or calls completed on time) with 95% confidence intervals. We will assess the impact of study arm on measures of severity at presentation, controlling for potential confounders collected at enrollment. We will describe standard of care patient follow-up behavior using results from Arm 3. We will also report surgery-related reasons for return to care beyond SSI. We will perform a sensitivity analysis to determine under what range of SSI rates the results are still valid.

Aim 5:

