The sample size for Phase 2 of this study was driven by Aim 4. We assume that the rates of SSI in the three arms will be similar (due to randomization), and we anticipate more patients with SSI will return to care in Arms 1 and 2 than in Arm 3. In each arm, we will enroll 364 patients. Assuming a 15% SSI rate, this translates to 55 SSI cases per arm. In Arm 3, we expect approximately 6% of all surgical patients to return with an SSI corresponding to 40% of all SSI infections. In Arms 1 and 2, we hypothesize twice as many patients with SSI (80%, n=44) will return. We would have an 81% power to detect a difference between the rate of patients that returned with SSI in Arms 1 and 2 (12%) as compared to Arm 3 (6%) with a two-sided test at the $\alpha=0.05$ significance level (Table 1).

	Arm 1	Arm 2	Arm 3
Description	Home visit on 10 th post-operative day (± 3 days)	Phone call on 10 th post-operative day (± 3 days)	Standard of care
Number per arm	364	364	364
Anticipated number with SSI	55	55	55
Hypothesized number to return with SSI days 7-14	44 (80%)	44 (80%)	22 (40%)
Overall hypothesized proportion that	0.12	0.12	0.06

will return on POD 7-14 with SSI			
--	--	--	--

RISKS AND DISCOMFORTS:

The study does not alter the standard of care in any way that increases risk to the patient. Risks to privacy are minimized by accessing data on password protected mobile phones, storing data on HIPAA-compliant servers, and de-identifying the database as soon as is practicable after the conclusion of the study period.

The primary risk associated with participation in this study is a breach in confidentiality, resulting in the disclosure of patient information. This risk is considered minimal; as unique codes will be used in place of participant names. All study staff will be trained in confidentiality. To further reduce the likelihood of a breach in confidentiality, all digital information will be stored in a password-protected document on an encrypted study computer, and all paper records will be stored in a locked file cabinet in a secure room at KDH.

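### Does the 81% power rest on an Arm 3 rate (6%) that the hospital's own 7.3% for obstetric patients contradicts?

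*Combined protocol and SAP*

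**What the plan says.** The Power Analysis takes an SSI rate of 15%, or 55 cases among 364 patients per arm. For standard care it says: "In Arm 3, we expect approximately 6% of all surgical patients to return with an SSI corresponding to 40% of all SSI infections". For Arms 1 and 2 it supposes that 80% of SSI patients return, which is 12% of the arm. It reports 81% power for 12% against 6%, two-sided at 0.05. Table 1 attaches a window to these proportions: returns on post-operative days 7-14.

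Subject Selection and Enrollment reports preliminary work at the same hospital: "7.3% of obstetric surgical patients and 3.1% of non-obstetric surgical patients returned to the hospital with an SSI". It gives no follow-up window, period or number of charts. Citing regional literature, it adds "we expect the true rate of SSI in patients receiving surgery KDH to be 10-20" per cent. Under Phase 2, participants come "from the adult female patient population receiving c-section surgery at KDH during a 14-month period".

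The Aim 4 analysis says "we will compare the proportion of patients who return for follow-up with an SSI in Arms 1 and 2 to Arm 3", with no window in that sentence. It also promises: "We will perform a sensitivity analysis to determine under what range of SSI rates the results are still valid".

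**The concern.** Phase 2 is a caesarean-only trial, and the plan holds a local figure for obstetric surgery. The Power Analysis nevertheless uses a lower figure, describes it as applying to all surgical patients, and does not say how the two relate. Because 6% lies between the obstetric 7.3% and the non-obstetric 3.1%, a reader may suspect that it was carried over from a mixed surgical population.

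The sample size was driven by this calculation. If standard care already brings back 7.3% and the intervention arms reach only 12%, the difference shrinks from 6 to 4.7 percentage points. Each comparison would then have about a 43% chance of missing the hypothesised effect, and a null result might be given more weight than it deserves because the protocol says 81%. The promised sensitivity analysis varies the SSI rate when the data are analysed. It does not address the standard-care return fraction or the planned power.

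**Working it through.** **Inputs.** From the Power Analysis and Table 1: 364 per arm, two-sided 0.05, SSI rate 15%, return fractions 40% (Arm 3) and 80% (Arms 1 and 2). From Subject Selection and Enrollment: 7.3% obstetric returns and a 10-20% range for the true SSI rate.

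**Formula.** For one intervention arm against Arm 3, with pooled variance under the null:

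power = Φ[(d − 1.96·s0)/s1], where d = p1 − p3, s0 = √(2·p̄(1 − p̄)/364), p̄ is the mean of the two rates, and s1 = √([p1(1 − p1) + p3(1 − p3)]/364).

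**Step 1: the plan's figure.** 0.15 × 0.40 = 0.06 and 0.15 × 0.80 = 0.12. Then d = 0.06, s0 = 0.02121, s1 = 0.02110, and (0.06 − 0.04157)/0.02110 = 0.873. Power is 80.9%, so the stated 81% is reproduced. The counts also agree: 22/364 = 6.0% and 44/364 = 12.1%.

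**Step 2: put 7.3% in Arm 3.** The Arm 3 rate is the SSI rate times the standard-care return fraction, so one of those two must move.

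| Reading | What moves | Rates compared | Power |
|---|---|---|---|
| A: SSI 15%, intervention return 80% | standard-care return becomes 0.073/0.15 = 48.7% | 7.3% v 12% | 57.5% |
| B: return 40% and 80% | SSI rate becomes 0.073/0.40 = 18.25% | 7.3% v 14.6% | 88.5% |

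For A: s0 = 0.02189, s1 = 0.02182, (0.047 − 0.04291)/0.02182 = 0.188. For B: s0 = 0.02315, s1 = 0.02299, (0.073 − 0.04537)/0.02299 = 1.202. Between them, with Arm 3 at 7.3% and 80% return in the intervention arms, power is 69.5% at 16% SSI and 79.5% at 17%.

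Reading B keeps the plan's hypothesis that the intervention doubles return, and its 18.25% lies inside the plan's 10-20%. Reading A keeps the plan's 15% but gives up the doubling. Nothing in the documents chooses between them.

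**Step 3: are 7.3% and 6% the same quantity?** Two things could separate them.

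- *Window.* Table 1 counts days 7-14; the chart review states no window. If a share f of the 7.3% falls on days 7-14, the comparable rate is 7.3% × f. It equals 6% at f = 0.06/0.073 = 82%. Taking f as an assumption, power against 12% is 81% at f = 82%, 71% at f = 90% and 57% at f = 100%.
- *Sampling error.* The number of charts is not given. The 95% limits, 0.073 ± 1.96·√(0.073 × 0.927/n), are 5.0-9.6% for an assumed 500 charts and 5.7-8.9% for 1,000. The lower limit reaches 6% only at n = 1.96² × 0.073 × 0.927/0.013² ≈ 1,538.

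The populations differ as well. Phase 2 is limited to adult caesarean patients living in the district and excludes anyone still in hospital at day 10; the chart review is described only as obstetric surgery.

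**Step 4: the range the plan already concedes.** With 40% and 80% return, power is 62.3% at 10% SSI (4% v 8%) and 91.5% at 20% (8% v 16%). The span of 57.5% to 88.5% opened by the 7.3% is of similar width to the span implied by the plan's own SSI range.

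**The case for a change.** The strongest case for a change is that a trial should be sized on its own population's data where they exist. The plan has such data, sets them aside without comment, and gives one power figure where the same local rate supports anything from 57.5% to 88.5%. The remedy would be cheap: a sentence, a small table and no extra patients. It can also be argued that the window explanation is not secure, because the Aim 4 text states none. Contact may come as late as day 13 ("Patients in Arm 2 will be phoned by the sCHW on the tenth post-operative day (± 3 days"), and those who "fail to return back to care within one week will be identified" takes the timeline to day 13 + 7 = 20, beyond Table 1's day 14.

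Part of this stands. The Power Analysis does not explain the 6% against the 7.3%, and the Aim 4 sentence does not repeat the window.

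The rest is weaker. The one-week rule selects referred patients for the interviews on barriers to care (Aim 6) and is not attached to the Aim 4 endpoint. The only window tied to the powered proportion is days 7-14. A single power figure for stated inputs is ordinary practice, and the inputs are set out so that any reader can vary them. A null result would be judged from the observed difference and its confidence interval, which do not depend on the planning rate. The mixed-population explanation for the 6% is conjecture: the documents give no such mix, and they derive the 6% as 15% × 40%.

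**Conclusion.** The concern does not call for a change. The 81% is arithmetically right for 12% against 6% with 364 per arm, and the documents do not show that the design fails to deliver it. The 7.3% is a related figure, but its window and sample size are unknown. It agrees with 6% if about 82% of the recorded returns fell on days 7-14, and 6% lies within its 95% limits if the review covered fewer than about 1,540 charts; both are assumptions that the documents neither support nor exclude. Taken at face value it moves power to 57.5% or to 88.5%, depending on which other input moves with it, so it is not evidence of an underpowered trial.

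What remains is an unexplained planning assumption. Explaining it would leave the 1,092 patients, the arms, the test of proportions and the Aim 4 conclusion as they are. Analysts can take days 7-14 from Table 1 as the window for the powered proportion, and the sensitivity analysis over SSI rates already acknowledges the main uncertainty. A sentence linking the two rates would help readers, but that is a matter of reporting preference.
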